6.2.4 On Study/Off-Intervention Evaluations

This trial will follow an intention-to-treat design. Subjects who discontinue study medication (see section 6.2.3) will be asked to continue to be followed for the remainder of the study, but will not be taking a study intervention. The following assessments will be performed at all on study/off-intervention visits:

- Hoehn & Yahr
- Concomitant medication review
- Orthostatics
- Height and weight
- Vital signs
- Physical examination
- Neurological examination
- MDS-UPDRS Motor Assessment
- Cognitive Assessments
- Behavioral Assessments
- Sleep Assessments
- Fall Assessments
- Speech Assessments
- Motor Assessments
- Blood draw

If participants are unable or unwilling to continue with the regularly-scheduled assessments after discontinuation of the study intervention, they will be encouraged to return to the study site for a final evaluation that will include the same assessments as listed above.

6.2.5 Final On-Study Evaluations

The final On-Study Evaluation will be comprised of the following assessments:

- Hoehn & Yahr
- Concomitant medication review
- Orthostatics
- Height and weight
- Vital Signs

FAST TZ-PD

Version 2.0

Version date: 11/12/2019

- Physical examination
- Neurological examination
- MDS-UPDRS Motor Assessment
- Cognitive assessments
- Behavioral Assessments
- Sleep assessments
- Fall Assessments
- Speech Assessment
- Motor Assessments
- Blood draw
- Drug accountability/compliance
- Adverse Event Review

6.2.6 Off-Study Requirements

No off-study requirements after the final evaluation will be employed for this study.

6.2.7 Pregnancy

Per the exclusion criteria, female who are pregnant will be excluded from this study. Terazosin has been designated a pregnancy category C medication by the FDA. Therefore, if a subject were to become pregnant while taking the active treatment, it is unclear if this would pose a risk to the developing fetus. As a result, females who are capable of becoming pregnant during the study should be screened with a urine-dipstick pregnancy test at their screening visit, prior to randomization, and at their 6-week visit. Females participants must also practice a highly effective method of contraception (i.e., oral contraceptives, a barrier method of birth control such as condoms or a diaphragm, intrauterine devices, partner with vasectomy, or sexual abstinence).

6.3 SPECIAL INSTRUCTIONS AND DEFINITIONS OF EVALUATIONS

6.3.1 Informed Consent

Written informed consent will be obtained from each subject before any study-specific procedures or assessments are performed and after the aims, methods, anticipated benefits, and potential hazards are explained. Written informed consent will be obtained from each participant by authorized personnel prior to undergoing screening and prior to randomization. The subject's willingness to participate in the study will be documented in writing in a consent form, which will be signed by the subject with the date of that signature indicated. The investigator will keep the original consent forms and copies will be given to the subjects. It will also be explained to the subjects that they are free to refuse entry into the study and free to withdraw from the study at any time without prejudice to future treatment. Written and/or oral information about the study in a language understandable by the subject will be given to all subjects. HIPAA guidelines for confidentiality and the principles of medical ethics will be adhered to during the study.

6.3.2 Protocol Violations

Protocol violations will be defined as any of the following:

- Inadequate or delinquent informed consent
- Inclusion/exclusion criteria not met
- Unreported serious adverse events
- Improper breaking of blinding
- Use of prohibited medications
- Missed visits
- Inadequate record keeping
- Non-compliance with study requirements

FAST TZ-PD

Version 2.0

Version date: 11/12/2019

6.3.3 Documentation of Parkinson's Disease

Participants must have a documented diagnosis of PD that fits with the UK Brain Bank Diagnostic Criteria (Appendix A).

6.3.4 Medical History

As part of the initial screening for inclusion in the study, participants will provide all comorbidities and their approximate time of diagnosis (Appendix B). At each visit, the participant will be asked to provide any newly diagnosed comorbidities.

6.3.5 Treatment History

Participants will be asked to provide a full history of any medications, over-the-counter products, herbal supplements, nutraceuticals, or devices that have been used for the treatment of PD or PD-related symptoms. They will also be asked to recollect (to the best of their knowledge) the timing of these treatments (i.e. when did they start the medication, when were dosage adjustments made, when was the treatment stopped). For medications that were used specifically for the treatment or relief of symptoms of PD, participants will be asked what the reason for discontinuation was, if applicable. Participants will also be asked to provide information about dosages, dosage form (capsule, tablet, etc) route of administration, dosing schedule (Appendix C)

6.3.6 Concomitant Medications/Treatments

In addition to PD-related treatment history, all concomitant medications they are currently taking. Participants will also be asked to provide information about dosages, dosage form (capsule, tablet, etc) route of administration, dosing schedule (Appendix D).

6.3.7 Protocol Amendments and Study Termination

All revisions and/or amendments to this protocol must be approved in writing by IRB. The Investigator will not make any changes to the conduct of the study or the protocol without first obtaining written approval from the IRB, except where necessary to eliminate an apparent immediate hazard to a study subject.

Any revisions to the protocol that will change the number or frequency of evaluations that a participant undergoes will require the participant to sign an updated written informed consent.

6.3.8 Clinical Assessments

- Hoehn & Yahr
 - Collected to measure disease severity as well as progression throughout study
- Orthostatics
 - Collected to measure if participants are having worsening orthostatic hypotension.
 - If orthostatic hypotension is present, this assessment will NOT be able to determine if it is secondary to the study medication or autonomic failure that occurs in PD.
- Physical examination
 - This will be a simple physical exam to measure the general health of the participant independent of their PD
- MDS UPDRS Part 3
 - This portion of the MDS-UPDRS specifically measures motor function. This will only be collected when subjects are in the practically defined "off-period" meaning that they have not taken their PD medications within 6 hours of the assessment
- MDS-UPDRS Part 4
 - This portion of the MDS-UPDRS will use historical and objective information to assess the motor complications of dyskinesia and motor fluctuations including off-state dystonias
- Vital signs/Height & Weight

FAST TZ-PD

Version 2.0

Version date: 11/12/2019

- Participants will have their heart rate, respiratory rate, blood pressure, and core body temperatures measured as well as their height and weight
- Neurological Exam

6.3.9 Laboratory Evaluations

Women of child-bearing potential will have a urine-dipstick pregnancy test performed at their screening visit, their baseline/randomization visit, and at their 6 week visit. The site PI must verify each result and indicate that the results are “Negative” or “Positive”. If the results are “negative”, this indicates that the subject is not pregnant. If the results are “positive” this indicates that the subject is pregnant and must discontinue study drug.

The MRI studies are being conducted to perform MR Spectroscopy in an attempt to quantify ATP levels in the brain.

The blood draws are being conducted to collect red blood cells. These samples will be sent immediately to the lab of [name], where they will be analyzed to quantify ATP levels in the red blood cells.

6.3.10 Pharmacokinetic Studies

N/A

6.3.11 Other Laboratory Studies

All randomized participants will have the option of having their blood drawn at each visit. Within the informed consent documents, subjects will have the option to donate blood or not. The subjects will be informed that the blood samples are being collecting for the sake of bio-banking meaning that the blood is being collected without a specific assay in mind. It is possible that these samples will be used for genome-wide studies in the future as well as assays aimed at quantifying ATP levels in red blood cells.

6.3.12 Questionnaires

- MDS-UPDRS Part 1
 - This will measure Non-motor experiences of daily living
- MDS-UPDRS Part 2
 - This will measure Motor experiences of daily living
- The following cognitive assessments will be performed
 - Hopkins Verbal Learning Test (HVLT)
 - Symbol Digit Modalities Test (SDMT)
 - Montreal Cognitive Assessment (MoCA)
- Pittsburgh Sleep Quality Index
 - Assessment of sleep quality
- The following behavioral assessments will be performed to test depression, compulsiveness & anxiety
 - Beck Depression Inventory (BDI)
 - Beck Anxiety Inventory (BAI)
 - Columbia Suicide Severity Rating Scale (C-SSRS)
 - Parkinson's Disease Questionnaire (PDQ-39)

6.3.13 Subject Adherence Assessments

The site pharmacies will document subject adherence at each visit by pill count.

FAST TZ-PD

Version 2.0

Version date: 11/12/2019

7 MANAGEMENT OF ADVERSE EXPERIENCES

The expected adverse experiences from use of TZ include orthostatic hypotension, palpitations, peripheral edema, nausea, asthenia, dizziness, headache, somnolence, nasal congestion, syncope, intraoperative floppy iris syndrome, and priapism. Participants who experience side effects that are found to be intolerable by the subject or the site investigator will discontinue study drug. If discontinuation of the study drug occurs in between visits, subjects will be encouraged to return to the site for their end of study assessment.

8 CRITERIA FOR INTERVENTION DISCONTINUATION

Study medication discontinuation will occur under the following circumstances:

- Completion of study
- Presence of orthostatic hypotension
- Blood pressure of $\leq 90/60$
- Participant initiates prohibited medication
- Participant reports unwillingness to continue with study due to intolerable side effects

Participants who discontinue study medication will be encouraged to undergo all remaining study assessments.

9 STATISTICAL CONSIDERATIONS

9.1 Outcomes

9.1.1 Primary Outcome (including definition)

The primary outcome measure will be the safety and tolerability of TZ in the select patient population. This will be assessed by comparing the number of participants in each group that experience drug-related adverse drug events as well as assessing the rate of drop out in each group.

To assess the mean change in systolic and diastolic blood pressures at 6 weeks and 12 weeks between the active and placebo groups.

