We will randomize 20 PD patients to receive TZ or placebo. Ten of the participants will be randomized to receive TZ 5mg daily for 12 weeks and 10 participants will be randomized to receive a daily placebo for 12 weeks. This aim will generate data on safety and tolerability of TZ in a population of patients with PD. As an exploratory outcome, we aim to determine if treatment with TZ in patients with PD improves markers of energy metabolism. Furthermore, we will determine if cellular and cerebral ATP levels correlate with disease severity and progression. Participants will also participate in an assessment that will include, but is not limited to a motor exam, a neuropsychological assessment, and functional assessments. Clinical findings will be used to guide future clinical trials.

Interventions and Duration

Participants in this study will be randomized to receive either TZ 5 mg by mouth once daily or a matched placebo once daily. Once randomized, each participant will receive their assigned treatment for 12 weeks. Participants will be assessed via telephone for 3 weeks after their 2 week visit, then 6 weeks months after their baseline visit, then via telephone 9 weeks after their baseline visit, and their last visit will occur 12 weeks from their baseline visit. We anticipate that this study can be completed (study open to end of data analyses) within 9 months.

Sample Size and Population

This study will randomize 20 participants: 10 participants will be randomized to receive 5mg of TZ daily and 10 participants will be randomized to the placebo group. It is anticipated that no more than 35 participants will need to be screened to enroll these participants.

This study will include participants who are ≥ 40 years old who have a confirmed diagnosis of PD made by a neurologist and a Hoehn & Yahr score at baseline of < 4 . Participants will be excluded from this study if any of the following are true:

- Participants has orthostatic hypotension or a sitting blood pressure of $\leq 90/60$
- Participant is pregnant
- Participant has a deep brain stimulation device implanted
- Participant has a known allergy or sensitivity to terazosin
- Participant is concomitantly taking doxazosin, alfuzosin, prazosin, urapadil, or tamsulosin
- Participant has active drug or alcohol use or dependence that, in the opinion of the site investigator, would interfere with adherence to study requirements
- Participant is unable or unwilling to give written informed consent

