- b) All MDS-UPDRS Motor Assessments will be collected when the participant is in the practically defined OFF state, meaning they have not taken their dopaminergic PD medications for > 6 hours at the time of assessment; this assessment will be video recorded to ensure rater reliability
- c) Baseline assessments on day 1 will occur PRIOR to randomization or the study drug being dispensed after the site coordinator has determine the subject is still eligible for participation.
- d) This will be performed twice at the baseline visit: prior to administration of TZ and 3 hours after administration of TZ
- e) Only the Beck Depression, Beck Anxiety, and C-SSRS will be assessed at the screening visit, per exclusion criteria
- f) At the Week 2 visit only the PDQ-39 will be assessed.

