6.2 Timing of Study Activities

6.2.1 Screening/Pre-Randomization Evaluations/procedures

Individuals identified at each site to potentially be eligible for inclusion will first be informed about the study and asked if they wish to receive more information. If the subject answers in the affirmative, approved staff will first go through the informed consent document with the subject and answer any questions that the subject may have. Specifically, the participant will be informed that signing this informed consent document does not guarantee that they will be included in the study. It simply allows the study sites to perform the necessary screening procedures to determine if the participant is eligible for randomization. If the participant signs the informed consent document, the participant will then be screened. This will include the following assessments:

- Review of inclusion/exclusion criteria
- Documentation of PD
- Hoehn & Yahr
- Review of concomitant medications/prohibited medications
- Orthostatics
- Medical history
- A physical exam
- Neurological exam
- Body weight and height
- Vital signs
- MDS-UPDRS Motor assessment
- Beck Depression Inventory, Beck Anxiety Inventory, Columbia-Suicide Severity Rating Scale

If the participant is found to be eligible for randomization based on this screening visit, their first baseline visit will be scheduled. The baseline visit must be scheduled within 90 days of the initial screening visit. If the participant is unable to schedule their baseline visit within 90 days of the screening visit, they may still be eligible for inclusion, but they will need to be re-screened.

After all assessments are completed, the site investigator will review the available data and ensure that the participant is eligible for randomization. If so, the participant will be randomized at Day 1. They will then be dispensed their study treatment packs. The participants will then have their blood drawn and then have their MRI. Immediately following this initial MRI, they will take their first dose of TZ 1mg or placebo. They will then wait 3 hours from that time, during which the other study assessments may be completed. After three hours from the time that they took their TZ, they will have their blood drawn again, and will then undergo another MRI study.

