9.1.2 Secondary Outcome(s)

- Mean change in systolic and diastolic blood pressure from baseline to 6 weeks and 12 weeks
- Prevalence of falls between placebo and active group
- Prevalence of intolerable side effects between placebo and active group
- Prevalence of study discontinuation between placebo and active group
- Differences in overall compliance between placebo and active group

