9.2 Sample Size and Accrual

This is a pilot study and the sample size was chosen based on available funding and resources

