9.4 Data Analyses

The following outcome measures will be analyzed under an intention-to-treat protocol. All randomized individuals will be included regardless of their final treatment status.

- Primary Outcome
 - Rate of drop out between groups
 - Chi-square
 - Rate of adverse events between groups
 - Chi-square
- Secondary outcomes
 - Prevalence of orthostatic hypotension between placebo and active group
 - Chi-square
 - Prevalence of falls between placebo and active group
 - Chi-square
 - Differences in overall compliance between placebo and active group
 - Linear mixed effect models that includes compliance at each study visit for each participant
- Exploratory outcomes
 - Difference in ATP levels in red blood cells and brain within subjects before and after taking study drug on day 1
 - Paired samples t-test
 - Difference in ATP levels in red blood cells and brain within subjects at 6 and 12 weeks compared to baseline reading

- Paired samples t-test
- Difference in ATP levels in red blood cells and brain between groups at 6 weeks and 12 weeks
 - Independent samples t-test
- Slope of change over 12 weeks of the MDS-UPDRS Part 1
 - LMER
- Slope of change over 12 weeks of the MDS-UPDRS Part 2
 - LMER
- Slope of change over 12 weeks of the MDS-UPDRS Part 3
 - LMER
- Slope of change over 12 weeks of the MDS-UPDRS Part 4
 - LMER
- Absolute change over 12 weeks of the MDS-UPDRS Parts 1, 2, 3, 4, and TMS
 - Independent samples t-tests
- Slope of change over 12 weeks of MDS-UPDRS TMS (direct comparison for efficacy)
 - LMER
- Slope of change over 12 weeks of the Hoehn & Yahr Score
 - LMER
- Slope of change over 12 weeks of all cognitive assessments between placebo and active group
 - LMER
- Slope of change over 12 weeks of sleep assessments between placebo and active group
 - LMER
- Slope of change over 12 weeks of behavioral assessments between placebo and active group
 - LMER

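### The between-arm blood pressure comparison is stated as mean change with no adjustment for baseline BP, although a pre-dose Day 1 reading is scheduled; at 10 v 10 this usually costs some precision

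*Combined protocol and SAP*

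**What the plan says.** Section 9.1.1 gives the comparison as "To assess the mean change in systolic and diastolic blood pressures at 6 weeks and 12 weeks between the active and placebo groups", and section 1.2 uses the same wording for the secondary objective. Section 9.1.2 lists the outcome again among the secondary outcomes: "Mean change in systolic and diastolic blood pressure from baseline to 6 weeks and 12 weeks". None of these places mentions baseline BP as a covariate.

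Section 9.4, which pairs outcomes with methods, has no entry for change in systolic or diastolic BP. Its only BP item is "Prevalence of orthostatic hypotension between placebo and active group", by chi-square. For the plan's other absolute-change outcome, the MDS-UPDRS parts, the method given is "Independent samples t-tests".

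The Schedule of Activities (6.1) marks vital signs and orthostatic measurements at Screening, Day 1, and weeks 2, 6 and 12. Its footnote c says "Baseline assessments on day 1 will occur PRIOR to randomization or the study drug being dispensed". Section 6.2.1 adds "The baseline visit must be scheduled within 90 days of the initial screening visit". The same section lets other study assessments be completed in the three hours after the first dose.

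On size, the synopsis says "This study will randomize 20 participants: 10 participants will be randomized to receive 5mg of TZ daily", with 10 on placebo, and section 9.2 says "This is a pilot study and the sample size was chosen based on available funding and resources".

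**The concern.** A change score subtracts the whole of a single noisy baseline reading from follow-up. Unless baseline and follow-up are very highly correlated, that subtracts too much: a patient whose Day 1 reading was high by chance will tend to show a fall, whatever the treatment. Across arms this averages out in expectation. In a single trial of 10 v 10, with no stratification described in 4.5.4, the arms can differ in baseline BP by several mmHg, and the difference in mean change is then pushed the opposite way. This could mimic or mask part of a BP effect of terazosin.

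The synopsis gives the reason for measuring BP: the drug might worsen orthostatic hypotension in this population. The estimate and its interval are what a later trial would take from this outcome, so precision that the scheduled data can supply should not be given up without reason.

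**Working it through.** **Plan's own figure.** There is none to reproduce. The sample size rests on funding, and no SD, correlation, effect size or significance level is given for BP.

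**Inputs.** From the documents: n = 10 per arm, N = 20. Assumed: a two-sided 95% interval, the same SD (s) at each reading, correlation rho between Day 1 and follow-up BP from 0.3 to 0.9, s of 10 to 20 mmHg, and all 20 participants analysed.

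**Variances per participant.**
- Change from Day 1: 2s²(1 − rho).
- ANCOVA on Day 1 BP: s²(1 − rho²), multiplied by 1 + 1/(N − 4) = 1 + 1/16 = 1.0625 to charge for chance baseline imbalance.
- Variance ratio, ANCOVA to change: 1.0625 × (1 + rho)/2.

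**Interval-width ratio.** Take the square root and multiply by t(17)/t(18) = 2.110/2.101 for the lost degree of freedom. At rho = 0.5: √(1.0625 × 0.75) × 2.110/2.101 = 0.896.

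| rho | Width, ANCOVA on Day 1 ÷ change score |
|---|---|
| 0.3 | 0.835 |
| 0.5 | 0.896 |
| 0.7 | 0.954 |
| 0.8 | 0.982 |
| 0.9 | 1.009 |

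The ratio reaches 1 at rho of about 0.87. Simulation of 20,000 trials at each of three correlations gave mean width ratios of 0.894 (rho 0.5), 0.952 (0.7) and 1.006 (0.9).

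**In mmHg at rho 0.5.** With s = 15, the half-width for change is 2.101 × 15 × √(2 × 0.5 × 2/10) = 14.1. For ANCOVA it is 2.110 × 15 × √(0.75 × 1.0625 × 2/10) = 12.6. With s = 10 the pair is 9.4 and 8.4; with s = 20 it is 18.8 and 16.8.

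**Chance imbalance.** The standard error of the baseline difference is s√(2/10). At s = 15 this is 6.7 mmHg. A one-standard-error imbalance moves the difference in mean change by (1 − rho) times that amount, in the opposite direction: 0.5 × 6.7 = 3.4 mmHg at rho 0.5. Over s of 10 to 20 and rho of 0.3 to 0.8, the shift runs from 10 × 0.447 × 0.2 = 0.9 to 20 × 0.447 × 0.7 = 6.3 mmHg.

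**Does Screening BP add anything?** Suppose first that every pair of readings has the same correlation.
- ANCOVA on the mean of Screening and Day 1 gives width ratios of 0.812, 0.845, 0.870 and 0.880 at rho 0.3, 0.5, 0.7 and 0.8.
- Unadjusted change from that same mean has variance 1.5s²(1 − rho), so its width ratio is √0.75 = 0.866 at every rho.
- Averaging therefore supplies most of this gain. Relative to the averaged change score, ANCOVA gives 0.812/0.866 = 0.94 at rho 0.3, 0.845/0.866 = 0.98 at 0.5, 1.00 at 0.7 and 1.02 at 0.8.

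Now let Screening correlate 0.2 less with both Day 1 and follow-up; call that value q = rho − 0.2. The residual variance is s²[1 − (rho + q)²/(2(1 + q))]. The width ratios against change from Day 1 become 0.899, 0.964 and 1.019 at rho 0.5, 0.7 and 0.8. Day 1 alone gives 0.896, 0.954 and 0.982, so the averaged covariate is then no better.

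**The case against.** The strongest objection is that the plan names no BP-change analysis to criticise. Mean change is an outcome definition and does not exclude adjustment: regressing change on arm and baseline gives the same treatment effect as regressing follow-up on arm and baseline. This stands in part. A reader might infer that the plan prescribes an unadjusted t-test for BP. The documents do not say so; section 9.4 is silent, and the t-test there belongs to the MDS-UPDRS. What remains is that no place provides for adjustment, and that the natural reading of the outcome, alongside the method chosen for the comparable one, is a raw comparison. Filling the gap in 9.4 means choosing a model, and the choice should be deliberate.

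The second objection is that validity is not at stake. This is right. A reader might infer that regression to the mean biases the comparison. Under randomisation it affects both arms alike in expectation, and the interval already allows for chance imbalance. The loss is one of precision.

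The third is that the gain is uncertain. This also stands: no correlation is given, Day 1 adjustment gains little at rho 0.8, and it loses slightly above about 0.87. A reader might also infer a firm gain of 11% to 19% from adjusting for two pre-dose readings. That figure mixes averaging with adjustment and assumes that a Screening reading up to 90 days earlier predicts follow-up as well as Day 1 does, which nothing in the documents supports.

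**Conclusion.** The point holds in a modest form. The stated comparison makes no provision for baseline BP, pre-dose BP is scheduled, and an adjusted analysis would usually be more precise: about 16%, 10%, 5% and 2% narrower at rho 0.3, 0.5, 0.7 and 0.8, level near 0.87, and about 1% wider at 0.9. These figures assume equal SDs across readings and 20 analysed participants. Fewer completers would raise the penalty for the covariate a little.

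Its weight is limited. Because the BP sentence sits under 9.1.1, a reader might infer that BP change is a primary or the main safety outcome. The synopsis and section 9.1.1 assess the primary outcome by drug-related adverse events and dropout, while the synopsis, 1.2 and 9.1.2 all make BP change secondary. The trial is a pilot with no stated power, margin or BP hypothesis, so no planned decision turns on the gain.

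**What to change.** In section 9.4, add an entry for systolic and diastolic BP: the between-arm difference at weeks 6 and 12, with 95% confidence interval, from an ANCOVA at each visit or one repeated-measures model with arm, visit and their interaction, taking pre-dose Day 1 BP as covariate. Name the posture, since the orthostatic procedure yields supine, sitting and standing values, and use the same posture for covariate and outcome. Report raw mean change by arm as description.

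Define baseline BP as the Day 1 reading taken before the first dose. Reconcile footnote c of the Schedule of Activities with the sentence in 6.2.1 that allows other assessments after dosing.

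Using Screening BP as well is optional. If it is used, fix the choice before unblinding and state the assumption about its correlation with follow-up.

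The cost is wording, one degree of freedom, and a slight loss of precision if the correlation proves very high. No new measurement is needed.
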